#### **16.2.1. Delegation of Responsibility**

When specific tasks are delegated by an investigator, included but not limited to conducting the informed consent process, the investigator is responsible for providing appropriate training and adequate supervision of those to whom tasks are delegated. The investigator is accountable for regulatory violations resulting from failure to adequately supervise the conduct of the clinical study.

#### **16.2.2. Investigator Records**

The investigator is responsible for the preparation (review and signature) and retention of the records cited below. Records are subject to inspection and must be retained for a period of at least two (2) years (or according to local regulatory requirements) after the investigation is terminated or the date that the records are no longer required for purposes of supporting publications or regulatory submissions.

- All significant correspondence which pertains to the investigation
- Subjects' case history records, including: signed subject informed consent form; all relevant observations; observations of adverse device events; medical history; completed sponsor Case Report Forms; documentation of the dates and reasons for any deviation from the protocol
- Copies of Case Report Forms and clinical data

- Signed Investigator Agreement and recent curriculum vitae, both of which also must be submitted to the sponsor
- IRB/EC approval and discourse documentation. A copy of the IRB/EC approval must be submitted to the sponsor

### **16.3. *Institutional Review Board/ Ethics Committee***

A copy of the protocol, proposed Informed Consent form, other written subject information, and any proposed advertising material must be submitted to the EC for written approval. A copy of the written EC approval of the protocol and Informed Consent form must be received by the sponsor before recruitment of subjects into the study and shipment of investigational product.

The Investigator must submit and, where necessary, obtain approval from the EC for all subsequent protocol amendments and changes to the Informed Consent form. The Investigator must notify the EC of deviations from the protocol or SAEs and SADEs occurring at the site in accordance with local procedures.

The Investigator is responsible for obtaining annual EC approval and renewal throughout the duration of the study. Copies of the Investigator's reports and the EC continuance of approval must be sent to the sponsor.

### **16.4. *Sponsor Responsibilities***

All information and data sent to BSC concerning subjects or their participation in this study will be considered confidential by BSC. Only authorized BSC personnel or a BSC representative will have access to these confidential records. Authorized regulatory personnel have the right to inspect and copy all records pertinent to this study. Study data collected during this study may be used by BSC for the purposes of this study, publication, and to support future research and/or other business purposes. All data used in the analysis and reporting of this study will be without identifiable reference to specific subject name.

Boston Scientific will keep subjects' health information confidential in accordance with all applicable laws and regulations. Boston Scientific may use subjects' health information to conduct this study, as well as for additional purposes, such as overseeing and improving the performance of its device, new medical research and proposals for developing new medical products or procedures, and other business purposes. Information received during the study will not be used to market to subjects; subject names will not be placed on any mailing lists or sold to anyone for marketing purposes.

#### **16.4.1. *Sponsor Records***

The sponsor will maintain the following records:

- All correspondence which pertains to the investigation

- Signed investigator agreements and curriculum vitae
- System/procedure related Adverse Device Events
- All case report forms, including samples of subject informed consents, submitted by the investigator; investigational plan and report of prior investigations
- Hospital staff training and study visit reports
- The sponsor will own and store the clinical data generated under this protocol

### **16.5. Insurance**

Where required by local/country regulation, proof and type of insurance coverage, by BSC for subjects in the study will be obtained.

## **17. Monitoring**

Monitoring (on-site and remote) will be performed during the study to assess continued compliance with the protocol and applicable regulations. In addition, the monitor verifies that study records are adequately maintained, that data are reported in a satisfactory manner with respect to timeliness, adequacy, and accuracy, and that the Investigator continues to have sufficient staff and facilities to conduct the study safely and effectively. The Investigator/institution guarantees direct access to original or electronic source documents by BSC personnel, their designees, and appropriate regulatory authorities.

The study may also be subject to a quality assurance audit by BSC or its designees, as well as inspection by appropriate regulatory authorities. It is important that the Investigator and relevant study personnel are available during on-site monitoring visits or audits and that sufficient time is devoted to the process.

## **18. Potential Risks and Benefits**

### **18.1. Risks Associated with the study**

Patients enrolled in this study will not be exposed to any additional testing, visits or risks as compared to patients who are routinely implanted with the WATCHMAN device and not enrolled in this study. The study only collects data from procedures and visits that are performed as routine practice, based on the patient's clinical indications

### **18.2. Risks Associated with a standard WATCHMAN Implant & Procedure**

Even if the WATCHMAN implant is performed as part of clinical practice, for completeness of information we report here the section of the WATCHMAN Directions For Use listing the possible adverse events and possible adverse device effects associated with implantation of a WATCHMAN device, in alphabetical order:

1. • Air Embolism
2. • Allergic Reaction to Contrast Media/Meds
3. • Anemia Requiring Transfusion
1. • Arrhythmias
  - AV Fistula
2. • Bruising - Hematoma
1. • Cranial Bleed
  - Death
    1. • Device Embolization
    2. • Device Thrombus
  - Excessive Bleeding
  - Gastrointestinal Bleeding
3. • Groin Puncture Bleed
1. • Hypotension
1. • Inability to Move or Retrieve Device
2. • Infection/Pneumonia
1. ☐ Major Bleed Requiring Transfusion
2. • Pericardial Effusion
1. • Pleural Effusion
  - Post Procedure Anesthesia Effects
  - Pseudoaneurysm
2. • Pulmonary Edema
  - Stroke - Hemorrhagic
1. • Stroke - Ischemic
  - Systemic Embolism
2. • TEE Complications (throat pain, bleeding)
  - Thrombosis
  - Thrombus at Septal Puncture
3. • Transient Ischemic Attack (TIA)
  - Vasovagal Reactions

Some additional events that may be expected in catheterization procedures include:

- Pneumothorax
- Pulmonary Vein Obstruction

- Valvular or vascular damage

### **18.3. Risk Minimization Actions**

Additional risks may exist. Risks can be minimized through compliance with this protocol, performing procedures in the appropriate hospital environment, adherence to subject selection criteria, close monitoring of the subject's physiologic status during procedures and/or follow-ups and by promptly supplying BSC with all pertinent information required by this protocol.

### **18.4. Anticipated Benefits**

No direct patient benefit is expected from this study. Patients enrolled in this study will receive the same clinical care as patients who are routinely implanted with WATCHMAN and not enrolled in this study. However, results from the data collected during this study may improve the management of WATCHMAN patients in the future, therefore the subjects enrolled in this study may also benefit at a later stage.

The potential benefit of implanting the WATCHMAN device is its expected ability to prevent thromboembolic events originating in the LAA. The WATCHMAN device may protect against ischemic stroke and systemic thromboembolism. In subjects implanted with the device, the elimination of Warfarin therapy may reduce bleeding complications, such as hemorrhagic stroke, associated with long-term anticoagulation.

## **19. Informed Consent**

Subject participation in this clinical study is voluntary. Informed Consent is required from all subjects or their legally authorized representative. The Investigator is responsible for ensuring that Informed Consent is obtained prior to any procedures and/or testing, or data collection.

The obtaining and documentation of Informed Consent must be in accordance with the principles of the Declaration of Helsinki, ISO 14155, any applicable national regulations, and local Ethics Committee and/or Regulatory authority body, as applicable. The ICF must be approved by the center's IRB, or central IRB, if applicable.

Boston Scientific will provide a study-specific template of the ICF to investigators participating in this study. The ICF template may be modified to meet the requirements of the investigative center's EC and local regulations. Any modification requires approval from BSC, or its representative, prior to use of the form. The ICF must be in a language understandable to the subject and if needed, BSC will assist the center in obtaining a written consent translation. Translated consent forms must also have EC approval prior to their use. Privacy language shall be included in the body of the form or as a separate form as applicable.

The process of obtaining Informed Consent shall:

- be conducted by the Principal Investigator or designee authorized to conduct the process,
- include a description of all aspects of the clinical study that are relevant to the subject's decision to participate throughout the clinical study,
- avoid any coercion of or undue influence of subjects to participate,
- not waive or appear to waive subject's legal rights,
- use native language that is non-technical and understandable to the subject or his/her legal representative,
- provide ample time for the subject to consider participation and ask questions if necessary,
- ensure important new information is provided to new and existing subjects throughout the clinical study.

The ICF shall always be signed and personally dated by the subject or legal representative and by the investigator or an authorized designee responsible for conducting the informed consent process. If a legal representative signs, the subject shall be asked to provide informed consent for continued participation as soon as his/her medical condition allows. The original signed ICF will be retained by the center and a copy of the signed and dated document and any other written information must be given to the person signing the form.

Failure to obtain subject consent will be reported by BSC to the applicable regulatory body according to their requirements (e.g., FDA requirement is within 5 working days of learning of such an event). Any violations of the informed consent process must be reported as deviations to the sponsor and local regulatory authorities, as appropriate.

If new information becomes available that can significantly affect a subject's future health and medical care, that information shall be provided to the affected subject(s) in written form via a revised ICF or, in some situations, enrolled subjects may be requested to sign and date an addendum to the ICF. In addition to new significant information during the course of a study, other situations may necessitate revision of the ICF, such as if there are amendments to the protocol, a change in Principal Investigator, administrative changes, or following annual review by the IRB. The new version of the ICF must be approved by the IRB/EC. Boston Scientific approval is required if changes to the revised ICF are requested by the center's IRB/EC. The IRB/EC will determine the subject population to be re-consented.

## 20. Safety Reporting

Adverse event definitions are provided in Table 5.

**Table 5: Adverse Event Definitions**

Term	Definition
Adverse Event (AE)  Ref: ISO 14155-2011  Ref: MEDDEV 2.7/3 12/2010	Any untoward medical occurrence, unintended disease or injury, or any untoward clinical signs (including an abnormal laboratory finding) in subjects, users or other persons, whether or not related to the investigational medical device.  NOTE 1: This includes events related to the investigational medical device or comparator.  NOTE 2: This definition includes events related to the procedures involved (any procedure in the clinical investigation plan).  NOTE 3: For users or other persons, this definition is restricted to events related to the investigational medical device.
Adverse Device Effect (ADE)  Ref: ISO 14155-2011  Ref: MEDDEV 2.7/3 12/2010	Adverse event related to the use of an investigational medical device  NOTE 1: This definition includes any adverse event resulting from insufficient or inadequate instructions for use, the deployment, the implantation, the installation, the operation, or any malfunction of the investigational medical device.  NOTE 2: This definition includes any event resulting from use error or from intentional misuse of the investigational medical device.
Serious Adverse Event (SAE)  Ref: ISO 14155-2011  Ref: MEDDEV 2.7/3 12/2010	Adverse event that: 
 
○ Led to death,
 
○ Led to serious deterioration in the health of the subject, that either resulted in:               
 
○ a life-threatening illness or injury, or
 
○ a permanent impairment of a body structure or a body function, or
 
○ in-patient or prolonged hospitalization of existing hospitalization, or
 
○ medical or surgical intervention to prevent life-threatening illness or injury or permanent impairment to a body structure or a body function                   
 
○ Led to fetal distress, fetal death, or a congenital abnormality or birth defect.
 
 
 
 
 
 NOTE 1: Planned hospitalization for a pre-existing condition, or a procedure required by the clinical investigational plan, without serious deterioration in health, is not considered a serious adverse event.
Serious Adverse Device Effect (SADE)  Ref: ISO 14155-2011  Ref: MEDDEV 2.7/3 12/2010	Adverse device effect that has resulted in any of the consequences characteristic of a serious adverse event.

**Table 5: Adverse Event Definitions**

Term	Definition
Unanticipated Serious Adverse Device Effect (USADE)  Ref: ISO 14155-2011  Ref: MEDDEV 2.7/3 12/2010	Serious adverse device effect which by its nature, incidence, severity, or outcome has not been identified in the current version of the System Guide of each device model  NOTE 1: Anticipated serious adverse device effect (ASADE) is an effect which by its nature, incidence, severity or outcome has been identified in the current version of the System Guide of each device model
Device Deficiency  Ref: ISO 14155-2011  Ref: MEDDEV 2.7/3 12/2010	A device deficiency is any inadequacy of a medical device with respect to its identity, quality, durability, reliability, safety or performance.  NOTE 1: Device deficiencies include malfunctions, misuse or use errors, and inadequate labeling.

Abbreviations: EC=Ethics Committee; IRB=Institutional Review Board

### **20.1. Investigator Reporting Requirements**

When reporting an Adverse Event the investigator will indicate the diagnosis of the event and correlating signs and symptoms on the adverse event case report form. Individual signs and symptoms and treatment/intervention/diagnostic testing should not be reported as separate adverse events, instead be reported as supporting documentation on the AE CRF. Additionally, it is not necessary to report an underlying disease that was present at baseline (i.e., CHF, AF, hypertension, chronic anemia, etc.). However, any increase in the severity of the underlying disease may require reporting, if at the determination of the investigator, it is relevant to the study. If possible, death should not be recorded as an AE, but should only be reflected as an outcome of a specific SAE (see Table 5 for AE definitions).

Adverse experiences that require reporting by the investigator to the sponsor include any adverse event with clinical symptoms that could possibly be contributed to any of the following:

4. The WATCHMAN device;
5. The WATCHMAN implant procedure;
6. The use of medications including warfarin, or other equivalent oral anticoagulant per institution's protocol, clopidogrel or aspirin (i.e., gastrointestinal bleeding due to warfarin or an allergic reaction to clopidogrel);
7. Any WATCHMAN related procedures (i.e., clinical complications from TEE or other procedure required by labeling)

The following adverse events will also be reported:

8. Neurological events including, but not limited to, stroke, TIA or seizure which are not pre-study conditions
9. Any events possibly related to stroke/TIA, systemic embolization, death, etc.

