#### **11.4. LAA Imaging (e.g. TEE/CT/MRI)**

Prior to implantation with the WATCHMAN device, an implant TEE (or alternative imaging method) is a clinical standard to confirm there is no thrombus in the LAA or left atrium. The implant LAA imaging will also allow the investigator to obtain proper measurements of the LAA to correctly size the device, confirm device release criteria are met prior to device release, and to confirm adverse events have not occurred during the implant procedure (i.e., pericardial effusion). If an intracardiac thrombus is visualized by echocardiographic imaging, the patients will not be implanted. Re-assessment may be scheduled per physician's discretion.

The first control LAA imaging, normally between 1-3 months post-implant, is a clinical standard after the WATCHMAN procedure, it is conducted to assess flow through and around the WATCHMAN device, to ensure sealing and to verify there is no thrombus on the surface of the device prior to stopping dual platelet inhibition or warfarin. Additional LAA imaging may be conducted at the discretion of the investigator and according to center's practice.

Certain information from TEEs conducted during the course of the study will be captured on the study case report forms, including: heart rhythm; valve status; pericardial status; atrial septum characteristics; LAA size and type of anatomy; thrombus assessment.

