#### **11.5. Implant Procedure**

The implant procedure should be performed using standard of care methods established by the investigational center (e.g. sterile technique, personnel requirements, etc.). Implantation of the WATCHMAN LAA Closure Device should only be performed by physicians trained in percutaneous and transseptal procedures who have completed the WATCHMAN training program. Refer to the WATCHMAN LAA Closure Technology

Directions for Use for detailed instructions regarding the implantation and use of the WATCHMAN technology. The following will be assessed during implant procedure and documented on case report forms for enrolled subjects:

- WATCHMAN Device and Access System usage information, including device size and compression post-implant;
- LAA imaging (as described in section 11.4): LAA measurements; intracardiac thrombus, device position, LAA seal, thrombus on the device surface;
- Concomitant procedures;
- Current medical status; vital signs; AF status;
- Current medication regimen for the use of antiplatelet and anticoagulation medications;
- Serious adverse events and adverse events during implant procedure. Data to be collected for peri-procedural complications include, but are not limited to:
  - Cardiovascular events: pericardial effusion, cardiac tamponade, bleeding, stroke (ischemic/non-ischemic), TIA, systemic embolism (please refer to Appendix A for definitions of stroke/TIA and classification of bleeding events)
  - ICU : Length of stay
  - Conventional care unit: Length of stay
  - Device/procedure related complications

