### 16.2. *Investigator Responsibilities*

The Principal Investigator of an investigational center is responsible for ensuring that the study is conducted in accordance with the Clinical Study Agreement, the investigational plan/protocol, ISO 14155, ethical principles that have their origins in the Declaration of Helsinki, any conditions of approval imposed by the reviewing IRB/EC, and prevailing local and/or country laws and/or regulations, whichever affords the greater protection to the subject.

The Principal Investigator's responsibilities include, but are not limited to, the following.

- Prior to beginning the study, sign the Investigator Agreement and Protocol Signature page documenting his/her agreement to conduct the study in accordance with the protocol.
- Provide his/her qualifications and experience to assume responsibility for the proper conduct of the study and that of key members of the center team through up-to-date curriculum vitae or other relevant documentation and disclose potential conflicts of interest, including financial, that may interfere with the conduct of the clinical study or interpretation of results.
- Make no changes in or deviate from this protocol, except to protect the life and physical well-being of a subject in an emergency; document and explain any deviation from the approved protocol that occurred during the course of the clinical investigation.
- Create and maintain source documents throughout the clinical study and ensure their availability with direct access during monitoring visits or audits; ensure that all clinical-investigation-related records are retained per requirements.
- Ensure the accuracy, completeness, legibility, and timeliness of the data reported to the sponsor in the CRFs and in all required reports.
- Record, report, and assess (seriousness and relationship to the device/procedure) every adverse event and observed device deficiency.
- Report to BSC, per the protocol requirements, all SAEs and device deficiencies that could have led to a SADE.
- Report to the IRB/EC and regulatory authorities any SAEs and device deficiencies that could have led to a SADE, if required by the national regulations or this protocol or by the IRB/EC, and supply BSC with any additional requested information related to the safety reporting of a particular event.
- Allow the sponsor to perform monitoring and auditing activities, and be accessible to the monitor and respond to questions during monitoring visits.

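### Section 20.1 attaches a symptom condition to device- and procedure-related event reporting that other sections do not, so silent, non-serious imaging findings may be recorded unevenly

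*Combined protocol and SAP*

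**What the plan says.** Section 20.1 opens its list of reportable events with "Adverse experiences that require reporting by the investigator to the sponsor include" and then "any adverse event with clinical symptoms that could possibly be contributed to any of the following". Four sources follow: the device, the implant procedure, medication such as anticoagulants and antiplatelets, and other WATCHMAN-related procedures. A second list (items 8 to 11) adds, without a symptom condition, neurological events, events possibly linked to stroke/TIA, systemic embolization or death, thrombosis, and bleeding that needs intervention or transfusion. Pericardial effusion and device embolization or migration appear in neither list.

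Other parts of the protocol are broader:

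- Table 5 counts as an adverse event "any untoward clinical signs (including an abnormal laboratory finding) in subjects, users or other persons".
- Section 16.2 tells the investigator to "Record, report, and assess (seriousness and relationship to the device/procedure) every adverse event and observed device deficiency".
- Section 11.4 uses implant imaging to "confirm adverse events have not occurred during the implant procedure (i.e., pericardial effusion").
- Section 11.5 requires on the case report forms "Serious adverse events and adverse events during implant procedure. Data to be collected for peri-procedural complications include, but are not limited to" a list that begins "Cardiovascular events: pericardial effusion, cardiac tamponade, bleeding, stroke" and ends with complications related to the device or the procedure.
- Section 11.6 collects serious and non-serious adverse events since the previous visit, at clinic visits and at phone contacts, with no mention of symptoms. Clinic visits also record device position from imaging.
- Table 6 places the judgement of seriousness and device relationship on the adverse event eCRF. Section 21.1 has the sponsor's medical safety group classify events.

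Sections 7 and 12.2 name procedural complications among the analyses. Neither defines them or says which forms supply the count.

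**The concern.** Section 20.1 is the detailed instruction a site is likely to consult when deciding whether to open an adverse event form. Control imaging is expected at 1–3 months after implant, and silent findings such as a small effusion or a shifted device are foreseeable there. Under the wording of 20.1, a site could record such a finding in the imaging fields and stop. The finding would then carry no assessment of seriousness or device relationship, and no section says that an imaging field alone prompts sponsor review. A site working from Table 5 or Section 16.2 would file the form.

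Two sites with identical patients could therefore report different complication rates. The error runs one way, because the symptom condition can remove events but cannot add them. In a registry whose product is a set of descriptive rates with confidence intervals, such a bias passes directly into the result, and the interval does not reflect it.

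**Working it through.** **Step 1. Which events are exposed?** I took each type of finding and looked for a provision that captures it without a symptom condition.

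| Finding | Provision | Exposed? |
|---|---|---|
| Effusion during implant | 11.4 treats it as an adverse event; 11.5 names it for the CRF | No |
| Thrombus on the device | 20.1, item 10 (thrombosis) | No |
| Any event meeting a seriousness criterion | Table 6: AE eCRF within 2 business days | No |
| Any adverse event in an Attempt subject, up to withdrawal | 10.3: a form for every adverse event after consent | No |
| Non-serious, silent effusion found after implant | 11.6 and 16.2 say record; 20.1 does not list it | Yes |
| Non-serious, silent device migration or embolization found after implant | 11.6 and 16.2 say record; 20.1 does not list it; position is an imaging field | Yes |

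The exposed group is the last two rows: non-serious, asymptomatic findings, mainly after implant.

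**Step 2. Reproduce the plan's precision figure.** Table 3 assumes an event rate p = 5%. The half-width is 1.96 × √(p(1 − p)/n):

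- n = 500: 1.96 × √(0.0475/500) = 1.91 points (plan: 1.9)
- n = 750: 1.96 × √(0.0475/750) = 1.56 points (plan: 1.6)
- n = 1000: 1.96 × √(0.0475/1000) = 1.35 points (plan: 1.4)

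Table 3 reproduces.

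**Step 3. Illustrate a shortfall.** Let f be the share of true complications left unrecorded. The documents give no value for f, so every row except f = 0 rests on an assumption. The observed rate is 5% × (1 − f). With n = 1000 and 50 true events:

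| f (assumed) | Observed rate | 95% interval | Shift | Chance that the interval contains 5% |
|---|---|---|---|---|
| 0 | 5.0% | 3.65–6.35 | 0 | 94% |
| 5% | 4.75% | 3.43–6.07 | 0.25 points | 91% |
| 10% | 4.5% (50 × 0.9 = 45) | 3.22–5.78 | 0.5 points | 84% |
| 20% | 4.0% (50 × 0.8 = 40) | 2.79–5.21 | 1.0 point | 59% |

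The last column sums exact binomial probabilities over the outcomes whose Wald interval includes 5%. The shift would equal the planned half-width only at f = 1.35/5 = 27%. A shift below the half-width still costs coverage, because it is systematic.

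**The case against.** The strongest reply is that the protocol, read as a whole, already requires these events. Section 20.1 introduces its list with a word meaning that the list is not closed. Section 16.2 has an unconditional duty covering every adverse event, and Section 11.6 collects adverse events at each follow-up contact. A site that left a silent complication unrecorded would breach both. Source review by monitors (21.1) and data queries (13.1) may catch omissions. A displaced device might also qualify as a device deficiency, with its own form and a 14-business-day limit. One might add that item 9 reaches device embolization through systemic embolization.

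Much of this stands. A reader might infer that 20.1 makes only symptomatic events reportable. The text does not say so, and 16.2 contradicts it. A reader might also infer that a silent embolization escapes the serious-event timeline. Table 6 applies no symptom test, so an embolization meeting a Table 5 seriousness criterion is on that timeline. One that meets no criterion would not be on it under any wording of 20.1.

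The reply does not remove the conflict. If every adverse event were already reportable through the first list, the second list in 20.1 would be unnecessary. Its presence suggests that the first list is meant to limit. Within 16.2, the item on reporting to the sponsor refers back to the protocol's requirements and names serious events and certain device deficiencies, so for a non-serious event the operative detail is again 20.1. Section 18.2 lists device embolization and systemic embolism as separate risks, so item 9 is not a safe substitute.

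**Conclusion.** The concern holds in a limited form. Section 20.1 is narrower than Table 5 and Sections 11.5, 11.6 and 16.2, and the passages need to be reconciled. The exposure is to non-serious, asymptomatic imaging findings, mainly after implant. The consequence is possible uneven recording, with any bias running downward, in rates that the plan lists among its primary analyses.

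It would be tempting to conclude that the procedural-complication rate is understated. The documents do not support that as a fact. They do not give the share of complications that are silent and non-serious, nor how sites read 20.1, nor whether the count is drawn from adverse event forms alone. The fall from 5% to 4.5–4.0% assumes a true rate of 5% and that 10–20% of events go unrecorded. The resulting 0.5–1.0 point shift is smaller than the 1.35-point half-width at n = 1000. If procedural complications were taken to mean implant-period events only, the effect on that outcome would be smaller still, and the gap would fall mainly on device-related event rates during follow-up.

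The change is worth making because a stated rule conflicts with the rest of the protocol and correcting it costs very little.

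**What to change.** - **Section 20.1:** delete the words that require clinical symptoms, so that any adverse event possibly attributable to the four listed sources is reportable. This brings it into line with Table 5 and Sections 11.5, 11.6 and 16.2.
- **Section 20.1:** add one line stating that pericardial effusion and device embolization or migration found on imaging go on the adverse event form whether or not the subject has symptoms. Device thrombus needs no addition, since item 10 covers it.
- **Section 12.2:** state that procedural complications are counted from the adverse event forms together with the complication items on the implant case report form.

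Reporting symptomatic and imaging-only complications separately would be a matter of preference and is not needed to resolve the conflict.

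The cost is two wording changes in 20.1, one sentence in 12.2, some additional adverse event forms, and possibly a slightly less favourable complication rate. No visit or test is added.
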